6.7.5.10. Laryngeal Events

Laryngeal events are those events that have visible swelling in the mouth/tongue/lips or any of the following internal swelling symptoms: lump in throat (tightness), difficulty swallowing, change in voice, or difficulty breathing, as recorded in the e-diary.

6.7.5.11. Event Triggers

All event triggers for each subject-reported event will be included in listings of event data.

6.7.5.12. AE-QoL

The AE-QoL (Wechsler, Fulkerson et al. 2012) consists of 4 domains and a total score. Each item answered by the subject scores between 0 and 4 points depending on the answer option chosen by the subject. The first answer option gets 0 points, the second option 1 point, the third option 2 points, etc.

Dimensions	Item
Functioning	1. Impairment of work
	2. Impairment of physical activity
	3. Impairment of spare time activities
Fatigue/Mood	4. Impairment of social relations
	6. Difficulties of falling asleep
	7. Waking up during the night
	8. Feeling tired during the day
	9. Difficulties in concentrating
	10. Feeling downhearted
Fears/Shame	12. Feeling burdened at having swellings
	13. Fear of new suddenly appearing swellings
	14. Fear of increased frequency of swellings
	15. Ashamed to visit public places
	16. Embarrassed by the appearance of swellings
	17. Fear of long-term negative drug effects
Nutrition	5. General limitations in foods and eating
	11. Limitations in the selection of food and beverages
Total Score	Items 1 to 17

The AE-QoL domain scores and the AE-QoL total score are calculated using the following formula:

$$(\Sigma \text{ items})/(\text{max } \Sigma \text{ items}) \times 100$$

where

Σ items = Sum of answered item scores per CRF

max Σ items = Sum of the maximum possible score for the answered items (ie 4 × the number of completed items)

The calculated AE-QoL ranges from 0 (best) to 100 (worst).

Since only answered items are included in the computation (and the calculated domain and total scores are not raw scores but linear transformations to a 0 to 100 scale), the calculated scores are not highly influenced by missing items. An AE-QoL domain score should not be calculated if more than 1 item is left unanswered in that domain. The AE-QoL total score should not be calculated if more than 25% of items (> 4 items) are left unanswered. Note that subjects who do not work were instructed to leave question 1 blank. As long as that is the only question in the functioning domain that is missing, the functioning domain can still be calculated.

6.7.6. Derived Health Outcomes Endpoints

6.7.6.1. EQ-5D-5L

The EQ-5D-5L consists of the EQ-5D-5L descriptive system and the EuroQoL Visual Analogue Scale (EQ VAS). The descriptive system is comprised of 5 dimensions: mobility, self-care, usual activities, pain/discomfort, and anxiety/depression as shown in [Table 12](#). Each dimension has 5 levels: no problems, slight problems, moderate problems, severe problems, and extreme problems. The respondent is asked to indicate his/her health state by ticking (or placing a cross) in the box against the most appropriate statement in each of the 5 dimensions. This decision results in a 1-digit number to express the level selected for that dimension. The digits for 5 dimensions can be combined in a 5-digit number to describe the respondent's health state. For example, 11122 would represent the health state for someone who has no problems with mobility, self-care, or usual activities, but who has slight pain or discomfort and slight anxiety or depression.

Note that this study uses the questionnaire in its validated form for subjects to report their health status "*today*". If the subject has had an HAE event since their last visit, starting at Week 4, they complete it a second time reflecting back on their health status during a "*usual event*". On summary tables, the "*today*" and "*usual event*" questionnaire results should appear in different rows.

Table 12: EQ-5D-5L Dimensions (UK English Sample Version)

Dimensions	Item
Mobility	I have no problems in walking about
	I have moderate problems in walking about
	I am unable to walk about
	I have severe problems in walking about
	I am unable to walk about
Self-Care	I have no problems washing or dressing myself
	I have slight problems washing or dressing myself
	I have moderate problems washing or dressing myself
	I have severe problems washing or dressing myself
	I am unable to wash or dress myself
Usual Activities (eg, work, study, housework, family or leisure activities)	I have no problems doing my usual activities
	I have slight problems doing my usual activities
	I have moderate problems doing my usual activities
	I have severe problems doing my usual activities
	I am unable to do my usual activities
Pain/Discomfort	I have no pain or discomfort
	I have slight pain or discomfort
	I have moderate pain or discomfort
	I have severe pain or discomfort
	I have extreme pain or discomfort
Anxiety/Depression	I am not anxious or depressed
	I am slightly anxious or depressed
	I am moderately anxious or depressed
	I am severely anxious or depressed
	I am extremely anxious or depressed

Abbreviations: EQ-5D-5L = EuroQoL 5-dimensional, 5-level questionnaire; UK = United Kingdom.

The EQ VAS records the respondent’s self-rated health on a 20-cm vertical visual analog scale (VAS). The VAS is numbered from 0 to 100 with 0 meaning ‘the worst health you can imagine’ and 100 meaning ‘the best health you can imagine’. This information can be used as a quantitative measure of health as judged by the individual respondents. The EQ-5D-5L asks respondents to simply ‘mark an X on the scale to indicate how your health is TODAY’ and then to ‘write the number you marked on the scale in the box below’.

For each subject and visit, the 5-digit health state will be converted into a single summary index, the EQ-5D Index, using the EQ-5D-5L Index calculator with United States (US) value set (Besari, Md Noor et al. 2014). A manual for EQ-5D is available (van Reenen and Janssen 2015).

6.7.6.2. Treatment Satisfaction Questionnaire for Medication

The TSQM consists of 14 items of which 13 items are made up of 3 specific scales (effectiveness, side effects, and convenience) and a global satisfaction scale (global satisfaction). In addition, one item (Item 4) questions whether as a result of taking this medication, the subject experienced any side effects at all, which can be answered by yes or no. Scale scores are calculated for each scale and are transformed into scores ranging from 0 to 100, with higher scores indicating higher satisfaction.

The 14 questions are detailed in [Table 13](#).

Table 13: List of Questions for TSQM

Item #	TSQM Item
1 ^a	How satisfied or dissatisfied are you with the ability of the medication to prevent or treat your condition?
2 ^a	How satisfied or dissatisfied are you with the way the medication relieves your symptoms?
3 ^a	How satisfied or dissatisfied are you with the amount of time it takes the medication to start working?
4 ^b	As a result of taking this medication, do you currently experience any side effects at all?
5	How bothersome are the side effects of the medication you take to treat your condition?
6	To what extent do the side effects interfere with your physical health and ability to function (ie, strength, energy levels, etc.)?
7	To what extent do the side effects interfere with your mental function (ie, ability to think clearly, stay awake, etc.)?
8	To what degree have medication side effects affected your overall satisfaction with the medication?
9	How easy or difficult is it to use the medication in its current form?
10	How easy or difficult is it to plan when you will use the medication each time?
11	How convenient or inconvenient is it to take the medication as instructed?
12	Overall, how confident are you that taking this medication is a good thing for you?
13	How certain are you that the good things about your medication outweigh the bad things?
14 ^a	Taking all things into account, how satisfied or dissatisfied are you with this medication?

Abbreviations: TSQM = Treatment Satisfaction Questionnaire for Medication.

^a These items are scaled on a seven-point bipolar scale from “extremely dissatisfied” to “extremely satisfied”.

^b Item #4 is a dichotomous response option with a conditional skip to Item #9.

Source: [\(Atkinson, Sinha et al. 2004\)](#)

Note that higher scores indicate higher satisfaction as the seven-point scale for the individual items goes from 1 = extremely dissatisfied to 7 = extremely satisfied.

The scale scores, also with higher numbers indicating higher satisfaction, are calculated as:

Effectiveness

$$(((\text{Item 1} + \text{Item 2} + \text{Item 3}) - 3) \div 18) \times 100.$$

$$\text{If 1 item is missing: } (((\text{Sum of Available Items}) - 2) \div 12) \times 100.$$

Side Effects

If Item 4 answer is “No” then score = 100.

Else...

$[(\text{Sum of Item 5 to Item 8}) - 4] \div 16 \times 100$.

If 1 item is missing: $[(\text{Sum of Available Items}) - 3] \div 12 \times 100$.

Convenience

$[(\text{Sum of Item 9 to Item 11}) - 3] \div 18 \times 100$.

If 1 item is missing: $[(\text{Sum of Available Items}) - 2] \div 12 \times 100$.

Global Satisfaction

$[(\text{Sum of Item 12 to Item 14}) - 3] \div 14 \times 100$.

If Item 12 or Item 13 is missing:

$[(\text{Sum (the two completed items)}) - 2] \div 10 \times 100$

If Item 14 is missing:

$[(\text{Sum of Available Items}) - 2] \div 8 \times 100$.

If more than 1 item is missing from any subscale, then the subscale will not be calculated.

6.7.6.3. Work Productivity and Activity Impairment Questionnaire

WPAI outcomes are expressed as impairment percentages, with higher numbers indicating greater impairment and less productivity (ie, worse outcomes). There are 4 impairment scores. The scoring is as follows ([Reilly Associates 2002](#)):

1. Absenteeism: Percent work time missed due to health: $100 * [Q2 / (Q2 + Q4)]$.
2. Presenteeism: Percent impairment while working due to health: $100 * [Q5 / 10]$.
3. Work productivity loss: Percent overall work impairment due to problem:
 $100 * \{Q2 / (Q2 + Q4) + [(1 - (Q2 / (Q2 + Q4))) * (Q5 / 10)]\}$.
4. Activity impairment: Percent activity impairment due to health: $100 * (Q6 / 10)$.

where,

Q2 = hours missed due to health problems

Q3 = hours missed due to other reasons

Q4 = hours actually worked

Q5 = degree health affected productivity while working (circle a number from 0 to 10, where 10 is worst impairment)

Q6 = degree health affected regular activities (circle a number from 0 to 10, where 10 is worst impairment)

Q1 asks whether the individual works for pay (yes/no). If the answer to that question is ‘No’ then the subject is instructed to skip to Q6.

6.8. Handling of Missing Data

6.8.1. Imputation of Missing Efficacy Endpoints Post Study Treatment Discontinuation

The event rate used in the primary analysis will be based on the observed data until the time of treatment discontinuation, if applicable. For the primary analysis at the end of Part 1, missing data sensitivity analyses will be conducted for handling of data for subjects who discontinue study treatment prior to the end of Part 1 in 2 ways:

1. Using observed post-treatment discontinuation data where available without imputation for missing data. For this analysis, the event rate will be computed through the last date of observed data up to the Part 2 treatment start date/time, including data collected after treatment discontinuation.
2. Observed post-treatment discontinuation data will be used in combination with an imputed event rate for the time period, post-treatment discontinuation, where data were not observed. An imputed rate for the entire 24-week period will be a weighted average of the observed rate up to the last day of diary collection (including days post treatment discontinuation) and the imputed rate for the time after treatment discontinuation during which data were not observed, with weighting based on the fraction of days with observed vs. unobserved data. For this rate, actual diary data collected after discontinuation of study treatment will be included in the observed rate where it is available by extending the time period in the denominator of the event rate calculation to the last day that diary data were collected, even if past study treatment discontinuation. The only exception to this is if the subject started other prophylactic treatment after discontinuation of study treatment. In that case, actual diary data will be used up until the time of start of other prophylactic treatment.

For subjects for whom no diary data is missing post study treatment discontinuation, no imputation is necessary. An observed confirmed event rate will be computed to include data post study treatment discontinuation as applicable, as long as the subject did not start other prophylactic therapy.

For subjects with missing data post study treatment discontinuation, missing data will be imputed as follows:

$$f = \text{Fraction of Non-missing Data}$$
$$= \frac{\text{Date of Last Day of Diary Collection Prior to Any Other Prophylactic Treatment} - \text{Date of First Dose} + 1}{169}$$
$$r_{\text{observed}} = \text{Observed Monthly Attack Rate Regardless of Study Treatment Discontinuation}$$
$$= \frac{\text{Number of Events} * 28}{\text{Date of Last Day of Diary Collection Prior to Any Other Prophylactic Treatment} - \text{Date of First Dose} + 1}$$

$$r_{\text{imputed}} = \text{Imputed Monthly Attack Rate for the Unobserved Period}$$

= $\begin{cases} \text{if missing at random, impute from complete cases in same treatment group} \\ \text{if not missing at random, median value of highest (worst) quartile rate in same treatment group or subject observed rate, if worse} \end{cases}$

$$r_{analyzed} = f * r_{observed} + (1 - f) * r_{imputed}$$

As shown above, if a subject discontinues study treatment or withdraws from the study, the imputation of $r_{imputed}$ will differ depending on whether the data are considered missing at random or not missing at random based on the reason for study treatment discontinuation or study withdrawal as shown in Table 14. Data missing at random will be imputed using multiple imputation with 10 separate rounds of imputations, randomly selecting from observed confirmed event rates of other subjects in the treatment group who completed the treatment for Part 1. Data not missing at random will be imputed using the median event rate of subjects in the worst quartile of performance (ie, highest event rate quartile) with regard to the primary endpoint for the given treatment group or the subject's observed rate over the time period of available data, if worse.

Table 14: Reason for Study Treatment Discontinuation and Whether Data are Considered Missing at Random or Not

Missing Data Considered Missing at Random	Missing Data Considered Not Missing at Random
Subsequent determination that inclusion/exclusion criteria were not met	Laboratory abnormality or adverse event
Intercurrent illness or emergence of new illness/medical condition/pregnancy	Discontinuation due to QT prolongation
Subject noncompliance with study drug or procedures	Discontinuation due to rash
Subject withdrew consent	Perceived lack of efficacy
Other ^a	Other ^a
Sponsor discontinuation ^a	Sponsor discontinuation ^a
Investigator judgment ^a	Investigator judgment ^a

^a A review of discontinuations for sponsor discontinuation, investigator judgment, or other reason will be completed prior to unblinding of Part 1 data for determination of missing at random or not missing at random.

6.8.2. Other Sensitivity Analyses for Missing Data

The PP population analyses will serve as a sensitivity analysis for missing data by displaying the results of analysis for subjects who generally followed the protocol. Analysis of the primary efficacy endpoint based on the completers population will also serve as a sensitivity analysis for missing data by showing the event rate in subjects who completed Part 1 of the study.

6.8.3. Missing Start and Stop Dates for Prior and Concomitant Medication

For analysis of medications, a complete date should be established in order to identify medication as occurring during treatment or not. For the purpose of handling partially reported start and stop dates for medication the following algorithm will be applied:

- Missing start day, but month and year present:

If trial medication had been taken in the same month and year as the occurrence of the medication, then the start day of the medication will be assigned to the day of first dose of trial medication.

Otherwise the start day will be set to the first day of the month.

- Missing start day and month, but year present:

If trial medication had been taken in the same year as the occurrence of the medication, then the start date of the medication will be assigned to the date of first application of trial medication.

Otherwise the start day and month will be set to 01 January.

- Completely missing start date:

For HAE medications, the date will be set to corresponding HAE event date. For all other concomitant medications, a completely missing date will be set to the treatment start date (if prior to the medication end date) or otherwise will be set to the medication end date.

- Missing end day, but month and year present:

The day will be set to the last day of the month.

- Missing end day and month, but year present:

The end day and month will be set to the date of trial termination.

However, if trial termination year is greater than the year of the event/medication, then the day and month will be set to 31 December.

In subject data listings, start and stop date of medication will be displayed as reported on the eCRF.

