9. TREATMENT OF SUBJECTS

9.1. Description of Study Drug and Study Drug Product

BCX7353 is an oral, small molecule inhibitor of plasma kallikrein. All subjects will receive a dose of BCX7353 (150 or 110 mg) or matching placebo (Part 1 only) capsules for oral administration once daily for up to 104 weeks (placebo capsules will be administered for 24 weeks followed by once daily treatment with BCX7353 for up to 80 weeks). Study drug or investigational medicinal product (IMP) in this study consists of BCX7353 and placebo capsules.

The investigational active pharmaceutical ingredient (API) is BCX7353, which is supplied as 55 or 75 mg capsules in Parts 1 and 2 and as a 150 mg capsule in Part 3. The capsules are composed of the API (BCX7353) blended with the excipients pregelatinized starch, polyplasdone XL, colloidal silicon dioxide, and magnesium stearate in a gelatin capsule.

The matching placebo will also be provided as capsules to match the BCX7353 capsules. The matching placebo will contain microcrystalline cellulose and magnesium stearate.

In Parts 1 and 2, subjects will be instructed to take 2 capsules of study drug (55 or 75 mg capsules) together at the same time daily. In Part 3, subjects will take a single capsule of study drug (150 mg capsule) daily. After the study has been transitioned to a post-marketing study following marketing authorization of BCX7353, BCX7353 will be administered at the dose regimen that is approved in Japan.

Additional details for the chemical and physical characteristics of BCX7353 may be found in the IB.

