6.8.4. Missing Start Date, Stop Date, Severity, or Relationship for Adverse Event

The same conventions to address incomplete dates for prior and concomitant medications will also be used for AEs. Should an event have a missing severity or relationship, it will be classified as having the highest severity and/or strongest relationship to study treatment.

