10.1. Adverse Event Preferred Term and System Organ Class Summary Tables

The following are Part 1 safety endpoints and Part 2 primary endpoints:

- Number and proportion of subjects with a TEAE
- Number and proportion of subjects who discontinue due to a TEAE
- Number and proportion of subjects who experience a TESAE
- Number and proportion of subjects who experience a Grade 3 or 4 TEAE
- Number and proportion of subjects who experience a treatment-emergent Grade 3 or 4 laboratory abnormality.

In addition, the proportion of subjects with a treatment-emergent, treatment-related AE consistent with a drug rash will also be summarized

AEs will be mapped to the MedDRA version 19.1 preferred term (PT) and SOC. AEs are assessed by the investigator as Grade 1 (mild), Grade 2 (moderate), Grade 3 (severe), or Grade 4 (life-threatening) according to Division of Microbiology and Infectious Diseases (DMID) using the November 2007 criteria. If a subject experiences multiple events that map to a single PT, the greatest severity grade according to the DMID criteria and strongest investigator assessment of relation to study medication will be assigned to the PT for the appropriate summaries. All AEs will be listed for individual subjects showing both verbatim and preferred terms.

TEAEs are defined as AEs that occurred on or after first dose of study treatment, whether in Part 1 or Part 2, and will be assigned to the relevant treatment depending on when the TEAE began (Part 1 or Part 2 treatment). AEs occurring 30 days after the last dose for subjects who discontinue study treatment in Part 1 or up to 30 days after last dose in Part 2 will be considered as TEAEs and will be associated with Part 1 or Part 2 respectively. Note that investigators are not required to contact subjects after the last follow-up if it occurs prior to 30 days from last dose. All AEs that occurred prior to the initiation of study treatment or those recorded more than 30 days after the last dose of study treatment will be excluded from the tables but will be included in the listings.

Drug-related events are defined as those AEs that the investigator believes were possibly, probably, or definitely related to the study drug.

10.1.1. Summaries of Adverse Event Incidence Rates for All Subjects and Incidence Rates for Serious Adverse Events, Discontinuations due to Adverse Events, and Deaths

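### For subjects first randomised to placebo, the SAP's rule for year-only or missing adverse event start dates can move events from active drug to placebo

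*SAP*

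**What the plan says.** SAP 6.8.3 gives three start-date rules, written for medications.

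- **Day missing.** If trial medication was taken in the reported month, "then the start day of the medication will be assigned to the day of first dose of trial medication". Failing that: "Otherwise the start day will be set to the first day of the month".
- **Day and month missing.** The condition is "If trial medication had been taken in the same year as the occurrence of the medication". If it is met, "the start date of the medication will be assigned to the date of first application of trial medication". Failing that, 1 January of the reported year is used.
- **Nothing known.** For anything other than an HAE medication, "a completely missing date will be set to the treatment start date (if prior to the medication end date"), and otherwise to the end date.

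SAP 6.8.4 extends these rules: "The same conventions to address incomplete dates for prior and concomitant medications will also be used for AEs". It also puts a missing severity or relationship in the worst category. SAP 10.1 says that TEAEs "will be assigned to the relevant treatment depending on when the TEAE began (Part 1 or Part 2 treatment").

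Protocol 9.1 states: "Study drug or investigational medicinal product (IMP) in this study consists of BCX7353 and placebo capsules". Group 3 takes placebo in Part 1 and active drug from Day 169 (Protocol 9.4). In SAP Table 8 the placebo column holds Part 1 data only. SAP 6.6 resets baseline to the first active dose for placebo starters, and Table 9 gives them adjusted visits. Sections 6.8.3, 6.8.4 and 10.1 contain no matching reset for incomplete dates.

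**The concern.** The date rule suits a trial with one treatment period. Here Group 3 changes from placebo to active drug at Week 24, and the anchor for an unknown onset is the first dose of study medication, which for them is placebo. An event that began on active drug can therefore be dated to a placebo day and tabulated there.

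The Part 2 and Part 3 primary endpoints are mostly proportions of subjects with TEAEs of various kinds. A misplaced Group 3 event lowers the active count and raises the placebo count. The rates per 100 person-years in SAP 10.1.4 are affected as well, because the event moves and the exposure time stays where it was.

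**Working it through.** **Inputs.** Part 1 is Days 1–168, Part 2 starts on Day 169 and Part 3 on Day 365. Planned sizes are 8 per group, with Group 3 re-randomised 1:1, so about 4 per after-placebo column. The SAP states no figure on this point that could be reproduced.

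**Two readings of the year condition.** Literal: drug was taken at any time in that year. Dosing is daily for up to 104 weeks, so every calendar year on study qualifies. Narrow: the first dose fell in that year.

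**Example** (assumed first placebo dose 18 Mar 2019; +168 days gives Part 2 from 2 Sep 2019; +364 days gives Part 3 from 16 Mar 2020):

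| True onset, Group 3 | Recorded as | Literal | Narrow |
|---|---|---|---|
| 5 Nov 2019 (Part 2) | 2019 | 18 Mar 2019, placebo | 18 Mar 2019, placebo |
| 10 Feb 2020 (Part 2) | 2020 | 18 Mar 2019, placebo, wrong year | 1 Jan 2020, active |
| 10 Aug 2020 (Part 3) | 2020 | 18 Mar 2019, placebo, wrong year | 1 Jan 2020, active |
| 5 Nov 2019 (Part 2) | Nov 2019 | 18 Nov 2019, active | 1 Nov 2019, active |
| 20 Sep 2019 (Part 2) | Sep 2019 | 18 Sep 2019, active | 1 Sep 2019, placebo |
| 5 Nov 2019 (Part 2) | no date | 18 Mar 2019, placebo | 18 Mar 2019, placebo |

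The first row fails on both readings. In the last row the end-date limit in 6.8.3 does not help, because a Part 2 event always ends after Day 1.

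**Over all dates.** The rule was applied to every possible onset day, assuming first doses uniform over one calendar year, onsets uniform within each part, and no end date. The shares are conditional on the date being incomplete.

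| Missing | Reading | Part 2 onset dated to Part 1 | Part 3 onset dated to Part 1 |
|---|---|---|---|
| Day and month | literal | 100% | 100% |
| Day and month | narrow | 73.0% | 10.8% |
| Everything | – | 100% | 100% |
| Day only | literal | 2.0% | 0% |
| Day only | narrow | 7.5% | 0% |

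For year-only dates read literally, the imputed year contradicts the reported year in 72.7% of Part 2 and 100% (rounded) of Part 3 onsets. So 100 − 72.7 = 27.3% of Part 2 onsets share the year of first dose and go to the first dose on either reading. The rest of the narrow figure, 73.0 − 27.3 = 45.7%, comes from the 1 January fallback landing before Day 169.

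Day-only errors run both ways. Literally, 2.2% of Part 1 onsets move forward to Part 2 and 6.6% of Part 2 onsets move forward to Part 3. Narrowly, 4.1% of Part 3 onsets move back to Part 2.

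**Which columns change.** Groups 1 and 2 (16 of 24) keep their dose through Part 2 (SAP 4.1), so their events can land in the wrong part or month but not the wrong column. SAP 6.1 keeps 110-to-150 mg switchers in their Part 2 column. For them the exposed output is the post-switch AE listing, 16.2.7.12.ES.

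**Largest shift from one misdated event, planned sizes:**

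- Placebo: 1/8 = 12.5 points.
- After-placebo column: 1/4 = 25 points.
- All 110 mg or all 150 mg: 1/(8 + 4) = 8.3 points.
- All active: 1/24 = 4.2 points.

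**The case against.** The strongest reply is that this will hardly ever occur. Investigators document AEs as they become aware of them (Protocol 12.1.2), edit checks are planned (SAP 6.3), SAEs are reported within 24 hours, and a possible drug rash is to be evaluated within 24 to 36 hours. No safety hypothesis is tested. All of that stands and keeps the practical size small. It does not make the rule correct where it does apply.

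A second reply is that subjects count once per treatment (SAP 10.1.1). In Study BCX7353-302, 76.9% to 85.0% of subjects per arm had a TEAE (Protocol 5.3.1), so the any-TEAE proportion would often not move. That also stands: the shifts above are ceilings. The endpoint of graded laboratory abnormalities comes from laboratory assessments and is not touched.

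A third is that anchoring on first dose is conservative. It is, for an event that might predate treatment, because it makes the event treatment-emergent. For a choice between placebo and active drug in Group 3 it works the other way.

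A reader might infer more than the text supports:

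- *All incomplete dates are affected.* No. The day-missing rule replaces the day only, so the reported month and year stay.
- *The Week 52 dose change misattributes events in the tables.* No. The SAP's column convention prevents that.
- *An event recorded as 2020 in a subject first dosed in 2019 is always sent back to 2019.* Only on the literal reading.
- *Placebo is the wrong attribution in a switch month.* Not necessarily; it may be the likelier one. Preferring active drug there is a convention.

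**Conclusion.** The rule is wrong as written for one group and two kinds of date: Group 3 subjects whose AE start has only a year, or no date at all. If such an event began on active drug in the calendar year dosing started, it is counted under placebo on either reading of the year condition. On the literal reading every year-only event from Parts 2 and 3 goes there too, sometimes against the reported year.

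The ceilings of 12.5 points (placebo) and 25 points (after-placebo column) hold only if the misdated event is the subject's sole qualifying event in the column concerned, and they rest on planned sizes. Outside Group 3 the effect is on the part or month to which an event is assigned, which feeds the by-month summary, the time-to-event displays for rash and GI events, and the post-switch listing.

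Two assumptions remain. The SAP never says first dose of Part 1; that is the plain reading of first dose of trial medication and of treatment start date. The documents do not give the number of incomplete AE dates. The change is worth making because it is nearly free and the cells are very small.

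**What to change.** In SAP 6.8.4, replace the cross-reference for AE start dates with a separate rule:

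1. Never impute a start outside the reported month or year, or after the AE end date.
2. If the reported period contains the first dose of Part 1, Part 2 or Part 3 study drug, use the latest such dose that is not after the AE end date. Otherwise use the first day of the reported period.
3. For a completely missing start in a Group 3 subject, use the first active dose in Part 2, unless the end date or the visit at which the event was recorded shows that it began earlier.

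Under rules 1 and 2 no Group 3 event that began in Part 2 or 3 reaches placebo. If the reported period contains the first active dose, that dose or a later one is chosen; if not, the period's first day already lies after it.

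The cost is a few sentences and a small programming change. The downside is that some ambiguous events, including some that truly began on placebo, will count against active drug. State this as a deliberate conservative convention, in line with how 6.8.4 treats missing severity and relationship.
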